PK parameters will be listed and summarized by treatment descriptively.

The derived PK parameters (C_{max}, AUC, T_{max} and C_{min}) will be rounded to three significant digits.

The relationship between PK parameters and efficacy endpoints such as HiSCR may also be evaluated.

G. Biomarker Assessments

A summary of the absolute and change from Baseline value for each available biomarker variable will be presented by treatment group, visit, and period.

A listing will be provided for subjects who have biomarker assessments.

H. Photographic Assessments

A listing will be provided for subjects who received photography by visit.

I. Supplementary Analyses Related to COVID-19

In order to describe the impact of COVID-19 on the current study, the following will be summarized in the tables/listings:

- Subjects discontinued from the study due to COVID-19 related on the study exit form.
- Add a new table for protocol deviations due to COVID-19.
- Add information for TEAE (COVID-19) in Overall AE summary table.
- Subjects with study visits missed or altered (including home health visit, phone/video conferencing, other) due to COVID-19. This may include altered or cancelled study visits and data collections because of a temporary study site closure during certain time periods of the COVID-19 pandemic.
 - An additional sensitivity analysis of the primary endpoint will be performed in the ITT population based on the LOCF and NRI imputation method.
 - LOCF: For any week 12 assessments performed via altered study visits or missing due to COVID019, last prior unaffected lesion assessment will be carried forward to week 12.

 NRI: impute any week 12 assessments performed via altered study visits or missing due to COVID019 as non-responders.

X. Changes from the Protocol Planned Analyses

The following changes from the protocol planned analyses are noted in this plan:

Changes	Protocol	SAP
Updated Adverse Events of Special Interest (AESI) definition	Page 63: 7.2.3.3. Adverse Events of Special Interest (AESI) The following findings, as defined below, must be reported as AEs and will be considered adverse events of interest (AESI): Infections: For medically important infections, the organisms involved in the infection need to be determined whenever possible and be documented in the EDC. All local and national vaccination recommendations should be followed. Hepatic Transaminase Elevation: • Grade 3 or greater increased ALT or AST (>5 times the upper limit of normal) • Grade 2 or greater increased ALT or AST (>3 times the upper limit of normal) with elevation of bilirubin to >2 times the upper limit of normal or INR >1.5 Neutropenia, Lymphopenia, and Leuokopenia: • Grade 3 or greater neutropenia (<1 x 109/L) • Grade 4 lymphopenia (<0.2 x 109/L) • Grade 3 or greater leukopenia (WBC count <2 x 109/L) Creatine Phosphokinase Elevation: • Grade 3 or greater CPK increase (>5 times the upper limit of dosing) Hypersensitivity Reactions: • urticaria • angioedema Malignancies: • Any malignancies will be reported as AEs. HS Lesion Interventions: • Lesion interventions as described in Section 5.7 will be recorded as AE.	Adverse Events of Special Interest (AESI) include infections, hepatic enzyme elevations, neutropenia and lymphopenia, hypersensitivity/angioedema, creatine phosphokinase elevation, malignancies, and HS Lesion interventions. Infections: The subject incidence of infections, serious infections, severe infections (i.e., Grade 3+), and infections leading to subject withdrawal from the study will be summarized by treatment group. Infections will be identified by selecting terms with the Adverse Event System Organ Class of 'Infections and Infestations'. Hepatic transaminase elevations: The following lab abnormalities will be included in this category: • Grade 3 or greater increased ALT or AST (>5 times the upper limit of normal) • Grade 2 or greater increased ALT or AST (>3 times the upper limit of normal) with elevation of bilirubin to >2 times the upper limit of normal or INR >1.5 Neutropenia, lymphopenia and leukopenia: The following lab abnormalities will be included in this category: • Grade 3 or greater neutropenia (<1 x 109/L) • Grade 4 lymphopenia (<0.2 x 109/L) • Grade 3 or greater leukopenia (WBC count <2 x 109/L)

		Hypersensitivity reactions: The subject incidence of adverse events associated with hypersensitivity/angioedema and urticaria will be summarized by treatment group. Terms will be based on the Standardized MedDRA Query for hypersensitivity. Creatine Phosphokinase Elevation: Grade 3 or greater CPK increase (>5 times the upper limit of normal) Malignancies: Any malignancies will be reported as AEs. HS Lesion Interventions: Lesion interventions due to HS will be recorded in CP.
The handling of multiplicity issues has been modified	Page 67: To address the multiplicity issue with two dose groups, a fixed hierarchical testing sequence will be employed. The hypothesis testing will test the avacopan 30 mg vs. placebo first. If the test is significant at the $\alpha = 0.05$ level, the avacopan 10 mg vs. placebo will be tested at the $\alpha = 0.05$ level. If the test of avacopan 30 mg vs. placebo is not significant at the $\alpha = 0.05$ level, the avacopan 10 mg vs. placebo will be tested as an exploratory analysis.	For the primary efficacy endpoint testing, the avacopan 30 mg vs. placebo in HiSCR (H ₁₁) and the avacopan 10 mg vs. placebo in HiSCR (H ₁₂), a hierarchical procedure will be used to control the overall α at 0.05 level. That is if H ₁₁ is rejected at a 2-sided alpha level of 0.05, then the H ₁₂ will be tested at 2-sided alpha level of 0.05. For secondary efficacy endpoint testing, the avacopan 30 mg vs. placebo or the avacopan 10 mg vs. placebo will be tested separately with the α = 0.05 level, provided that the corresponding primary endpoint testing of the same dose level is significant. As the two drug doses are two independent families. And the outcome of the study is to select one dose, not 2 doses. A fixed hierarchical testing sequence will be employed.
The primary analysis population's name has been changed from mITT to ITT	Page 68: Modified Intent-to-Treat (mITT) Population	Intent-to-Treat (ITT) Population
Definitions of ITT, Safety and Per Protocol Populations.	Page 68:	Intent-to-Treat Population The Intent-to-Treat (ITT) Population will include all subjects who are

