3. STUDY DESIGN

The study is a randomized, double-blind, placebo-controlled, three-group Phase 2 trial in approximately 390 subjects with moderate to severe hidradenitis suppurativa (Hurley Stage II or III). Subjects will be randomized 1:1:1 to a treatment of 10 mg avacopan twice daily, 30 mg avacopan twice daily or placebo for 12 weeks. Other systemic treatments for HS including anti-TNF- α treatments are prohibited. Stable antibiotic therapy with doxycycline or minocycline is allowed as specified in the protocol. Subjects treated with 10 mg or 30 mg twice daily during the blinded, placebo-controlled 12-week treatment period (Period 1) will be followed by an additional 24-week, active treatment period (Period 2) during which they will continue to receive the same dose regimen, either 10 mg or 30 mg avacopan twice daily. Subjects on placebo who complete Period 1 will be re-randomized 1:1 to receive 10 mg or 30 mg avacopan twice daily in Period 2. During Period 2 the treatment assignment to 10 mg or 30 mg twice daily will not be disclosed to the subject, study site personnel or the Sponsor. Thereafter, all subjects will be followed for 8 weeks without study drug before they exit the study.

To obtain balance across treatment groups, a stratified randomization scheme will be implemented. The stratification factors and strata within each factor are listed below.

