8.3. Sample Size Determination

The study will enroll approximately 390 subjects. In two Phase 3 clinical trials with adalimumab (PIONEER I and II; [Kimball et al, 2016a](#)), the proportions of subjects in the placebo control group achieving a HiSCR at Week 12 were 26.0% and 27.6%, respectively. Hence, if the control group only receives placebo, one may assume a HiSCR at Week 12 of approximately 30%. The average HiSCR at Week 12 in the adalimumab groups in PIONEER I and II were 41.8% and 58.9%, respectively with an average of approximately 50% ([Kimball et al, 2016a](#)). The attrition rate throughout the trial is estimated to be approximately 7%. A sample size of approximately 130 subjects per treatment group (390 in total) at a Type I error rate of $\alpha = 0.05$ (two-sided) provides approximately 90% power to detect a 20% superiority of avacopan compared to the placebo control group in HiSCR at Week 12, assuming an HiSCR at Week 12 of 50% in the avacopan group.

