The Safety Populations will be analyzed according to the assigned treatment group. In the event that a subject receives a treatment regimen that does not correspond to the assigned treatment consistently, the subject will be included in the analysis group of the treatment actually received.

Pharmacokinetic Population

Pharmacokinetic (PK) population is a subset of the Safety population and includes all subjects with at least one measurable plasma pharmacokinetic concentration of avacopan or its metabolite M1.

The PK populations are defined for the two treatment periods as the following:

- The PK1 Population in Period 1 is a subset of the Safety1 population and includes all subjects with at least one measurable plasma pharmacokinetic concentration of avacopan or its metabolite M1 in Period 1.
- The PK2 Population in Period 2 is a subset of the Safety2 population and includes all subjects with at least one measurable plasma pharmacokinetic concentration of avacopan or its metabolite M1 in Period 2.

Subjects with major protocol deviation including PK deviation or compliance issues may be excluded from the PK analyses (i.e. descriptive statistics) upon agreement with the Sponsor on case by case basis but all data will be listed. Values that are excluded from the analysis will be footnoted appropriately.

K. Subgroup Analysis

Please see section VIII D for subgroup analysis.

L. Data Display Characteristics

Data displays produced for this study will include three types: summary tables, data listings, and figures.

Data listings will simply list the data recorded on the case report form (CRF) or derived for each subject. They will be ordered by treatment, subject number, and

time of assessment. Additional levels of ordering may be employed as appropriate. Data listings will not display subject initials.

In general, summary tables for the double-blind treatment period (Period 1) will be presented by treatment group:

- Placebo
- Avacopan 10 mg
- Avacopan 30 mg
- Avacopan Total (i.e., Avacopan 10 mg + Avacopan 30 mg)

Summary tables for the 24-week active treatment period (Period 2) will be presented by the following treatment group:

- Placebo to Avacopan 10 mg
- Placebo to Avacopan 30 mg
- Avacopan 10 mg
- Avacopan 30 mg
- Avacopan Total (i.e., Placebo to Avacopan 10 mg + Placebo to Avacopan 30 mg + Avacopan 10 mg + Avacopan 30 mg)

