- The Work Productivity and Activity Impairment Questionnaire: Specific Health Problem (WPAI:SHP), change from baseline to Week 12 (MMRM model, ANCOVA model)

For the other endpoints, only the primary analysis will be applied.

For the analysis of variables in Period 1, not by visit, such as: duration of flare, health-economic information on hospitalizations, emergency or urgent care visits,

and lesion interventions for HS, an analysis of covariance (ANCOVA) model with treatment, baseline value, Hurley Stage (Stage II vs. III), concomitant antibiotic therapy with allowed antibiotics (Yes vs. No), and anti-TNF drug use (Treatment naïve vs. Previous treatment) will be applied. Treatment comparisons between the avacopan group and the placebo control group will be presented.

2. Analysis of Secondary and Other Efficacy Endpoints in Period 2

The efficacy data for secondary and other endpoints by timepoint in Period 2 will be summarized using descriptive statistics in the ITT2 population.

For binary variables, Non-Responder Imputation will be used; for change from baseline variables, other than lesion counts endpoints, no missing data imputations will be performed.

For selected secondary efficacy endpoints specified above, a MMRM model including treatment group, visit, treatment-by-visit interaction, and randomization strata (Hurley Stage II or Hurley Stage III, previous anti-TNF-α drug use or anti-TNF-α drug naïve, concomitant antibiotic therapy use or not) as factors, and corresponding baseline as covariate will be applied in Period 2. Testing p-values, point estimates and corresponding 95% confidence intervals will be estimated for the difference the avacopan 30 mg vs. total placebo to avacopan group, and avacopan 10 mg vs. total placebo to avacopan group across visits in Period 2 using linear contrast from the model.

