For the analysis of time to loss of response (LOR), the treatment difference between the avacopan 30 mg vs. placebo to avacopan 30 mg, avacopan 10 mg vs. placebo to avacopan 10 mg, avacopan 30 mg group vs. avacopan 10 mg group, and placebo to avacopan 30 mg vs. placebo to avacopan 10 mg will be analyzed using the stratified log-rank test with the baseline Hurley Stage (Stage II vs. III), concomitant antibiotic therapy with allowed antibiotics (Yes vs. No), and anti-TNF drug use (Treatment naïve vs. Previous treatment) as the stratification variables. Subjects without LOR or lost follow-up will be censored at the date of the last assessment of number of HS lesions. Kaplan-Meier curves will be provided by treatment group.

IX. Safety Analyses

Safety analyses will be performed in the Safety Analysis Set using the actual treatment group.

A. Adverse Events

All subjects will be assessed regularly for potential occurrence of adverse events (AEs) throughout the study until the subject is off study. The Medical Dictionary for Regulatory Activities (MedDRA; Version 21.1) will be used to code all adverse events to a System Organ Class (SOC) and Preferred Term (PT).

A treatment-emergent AE (TEAE) in Period 1 is defined as any AE that occurs after the first dose of study treatment in Period 1 and before the date of first dose of study treatment in Period 2.

A treatment-emergent AE (TEAE) in Period 2 is defined as any AE that occurs after the first dose of study treatment in Period 2.

A treatment-emergent AE (TEAE) for all avacopan, is defined as any AE that occurs after the first dose of avacopan treatment in study.

The incidence of TEAEs will be summarized and tabulated by treatment group and period.

The severity of each AE will be assessed as mild, moderate, severe, lifethreatening, fatal, or death. Several occurrences of the same AE in one subject will be counted once and the one with maximum severity will be counted.

The relationship of each AE to the blind study medication will be classified as probably not related or possibly related. Several occurrences of the same AE in one subject will be counted once and the one with the maximum relationship to blind study medication will be counted. If an AE is missing the relationship to blind study medication, the event will be assumed to be probably related for analysis and summarization.

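### The exploratory Period 2 mixed model compares each dose with a 1:1 mix of both doses, so if the doses differ, neither contrast alone can be attributed to dose or to duration

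*SAP*

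**What the plan says.** Protocol section 3 randomises 1:1:1 in Period 1. In Period 2, subjects already on avacopan stay on their dose: "they will continue to receive the same dose regimen, either 10 mg or 30 mg avacopan twice daily". For the placebo arm, "Subjects on placebo who complete Period 1 will be re-randomized 1:1 to receive 10 mg or 30 mg avacopan twice daily in Period 2". At every Period 2 visit the continuous arms have therefore had 12 more weeks of avacopan than the switchers, and the switchers are about half on each dose.

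SAP VIII.E.2 (the Period 2 part of the secondary and other endpoint analyses) makes descriptive statistics the general approach. For selected secondary endpoints it adds a mixed model for repeated measures, with p-values, estimates and 95% confidence intervals for two contrasts: "the avacopan 30 mg vs. total placebo to avacopan group" and "avacopan 10 mg vs. total placebo to avacopan group across visits in Period 2". No dose-matched contrast and no 30 mg versus 10 mg contrast is listed for this model.

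The next paragraph of the same section handles time to loss of response differently. Its pairs include "avacopan 30 mg vs. placebo to avacopan 30 mg, avacopan 10 mg vs. placebo to avacopan 10 mg", followed by 30 mg versus 10 mg in the continuous arms and in the switchers. SAP VI.L also keeps the two switcher groups apart in the Period 2 summary tables.

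**The concern.** Period 2 can inform two questions: whether 12 more weeks on avacopan matter, and whether 30 mg does better than 10 mg. Comparing a single dose with a mixture of both doses puts the two questions into one number. If 30 mg is the better dose, the 30 mg contrast overstates the duration effect and the 10 mg contrast understates it. A reader who takes the contrasts as early versus delayed start at each dose could conclude that longer treatment helps at 30 mg and not at 10 mg, when the duration effect is the same at both.

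The affected endpoints are the continuous ones on the selected list: IHS4, modified Sartorius score, SF-36, EQ-5D-5L, HiSQOL, DLQI and WPAI:SHP. Because SAP VI.I describes the study's outcome as the selection of one dose, a contrast in which dose is mixed with duration is worth tidying up, even in an exploratory analysis.

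**Working it through.** **Inputs from the documents.** About 130 subjects per arm and 7% attrition (Protocol 8.3, SAP IV.C); 1:1:1 allocation, then 1:1 re-randomisation of placebo completers (Protocol section 3).

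**Assumptions.** The documents give no standard deviation, effect size or precision for the Period 2 contrasts. I work in SD units, let G range from 0.2 to 0.5, and take Period 2 groups of 130, 130, 65 and 65 (full retention). Effects are additive, and positive values mean improvement. Standard errors use the two-mean formula and ignore covariates.

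**1. The plan's own figure.** The only design figure is about 90% power for Week 12 HiSCR, 50% versus 30%. Power = Φ{[0.20 − 1.96√(2 × 0.4 × 0.6/n)] / √[(0.3 × 0.7 + 0.5 × 0.5)/n]}.
- n = 130: Φ(0.0809/0.0595) = 91.3%.
- n = 130 × 0.93 = 120.9: Φ(0.0765/0.0617) = 89.3%.

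The figure reproduces, so 130 per arm is a sound starting point. It says nothing about Period 2.

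**2. What the contrasts estimate.** Let m be the mean in the placebo-to-10 mg group. The other means are m + G (placebo-to-30 mg), m + T (continuous 10 mg) and m + T + G (continuous 30 mg). The pooled switchers have mean m + G/2.
- 30 mg contrast: (m + T + G) − (m + G/2) = T + G/2.
- 10 mg contrast: (m + T) − (m + G/2) = T − G/2.
- Either dose-matched contrast: T.

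If a share w of the switchers is on 30 mg, the planned contrasts become T + (1 − w)G and T − wG, so a modest departure from 1:1 changes little.

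**3. Illustrative values (SD units).**

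| T | G | 30 mg contrast | 10 mg contrast | Dose-matched |
|---|---|---|---|---|
| 0 | 0.4 | +0.2 | −0.2 | 0 |
| 0.2 | 0.4 | +0.4 | 0 | 0.2 |
| 0.4 | 0.4 | +0.6 | +0.2 | 0.4 |
| 0.4 | 0 | +0.4 | +0.4 | 0.4 |

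The 10 mg contrast turns negative only when T is smaller than G/2. With G = 0, both contrasts are clean duration contrasts.

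**4. Precision.**
- Planned contrast: √(1/130 + 1/130) = 0.124.
- Dose-matched contrast: √(1/130 + 1/65) = 0.152; ratio 0.152/0.124 = 1.22.
- Average of the two dose-matched contrasts: √[¼ × 2 × (1/130 + 1/65)] = 0.107.
- Continuous 30 mg versus 10 mg: √(2/130) = 0.124.
- Placebo-to-30 mg versus placebo-to-10 mg: √(2/65) = 0.175.

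Differences detectable with 80% power (multiply by 2.80) are 0.35 for a planned contrast, 0.43 for a dose-matched one and 0.30 for the average. With 121 per arm, the first three standard errors become 0.129, 0.157 and 0.111, and the ratio stays at 1.22.

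**5. Probability of a significant result.** For a true contrast δ this is Φ(δ/SE − 1.96) + Φ(−δ/SE − 1.96).
- T = 0, 30 mg contrast (δ = G/2): 13%, 23%, 36% and 52% for G = 0.2, 0.3, 0.4 and 0.5.
- T = G = 0.4: the planned 10 mg contrast (δ = 0.2) has 36% power; the dose-matched contrast (δ = 0.4, SE 0.152) has 75%.

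**The case against.** The strongest reply is that these contrasts are well defined, exploratory, and surrounded by material that answers the same questions.

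- **A reader might infer that the p-values cannot be interpreted.** That goes too far. Each tests a stated null: the mean on one continuous dose equals the mean of the placebo-start group. If the doses perform alike, it is a valid duration test that uses the whole comparator group.
- **A reader might infer that the analysis answers neither question.** Taken as a pair, it carries both: with equal weights the average of the two contrasts is T, and their difference is continuous 30 mg minus 10 mg. This stands for the point estimates. However, the SAP plans neither combination, and because the contrasts share a comparator, an interval for the average or the difference cannot be built from the two reported intervals alone.
- **A reader might infer that longer 10 mg treatment will look harmful.** That needs T smaller than G/2; otherwise the 10 mg contrast is only attenuated or zero. It also needs someone to label the contrast a duration effect, which the SAP does not do.
- **A reader might infer that the model merges the two switcher groups.** The text does not show this. It refers to a treatment-group factor and linear contrasts, and SAP VI.L defines four Period 2 groups, so the total may be an average over separate levels. The algebra in step 2 is the same either way.
- **Scope.** SAP VI.I treats comparisons outside the primary and ranked Week 12 tests as supportive or exploratory, without multiplicity control. Protocol 8.8.4 plans only summaries of these endpoints in Period 2, so the mixed model is an addition.

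These replies limit the point. They do not explain why the mixed model uses a mixed-dose comparator when the next paragraph of the SAP uses matched ones.

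**Conclusion.** The point holds for the Period 2 mixed model only. Each planned contrast combines the duration effect with half the dose difference, added for 30 mg and subtracted for 10 mg. When the doses differ, neither contrast taken alone can be attributed to dose or to duration.

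The shift is G/2 in either direction, and its actual size is unknown because the documents give no Period 2 effect. Over the illustrative range of G from 0.2 to 0.5 SD it is 0.10 to 0.25 SD. With no duration effect, that produces a significant 30 mg contrast 13% to 52% of the time.

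These figures rest on additive effects, a 1:1 mix of switchers, full retention, and Period 2 entrants who are comparable across the original arms. The algebra needs no sample size. Nothing here touches the primary endpoint, the ranked Week 12 tests, trial power, the four-group descriptive tables or the loss-of-response comparisons. It is a cheap improvement to an exploratory analysis.

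**What to change.** In SAP VIII.E.2, state that the four Period 2 groups are separate levels of the treatment factor. Replace the two contrasts with the four pairs already listed for time to loss of response:

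- 30 mg versus placebo-to-30 mg;
- 10 mg versus placebo-to-10 mg;
- 30 mg versus 10 mg;
- placebo-to-30 mg versus placebo-to-10 mg.

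Add the average of the first two as the overall duration estimate. The last pair shows the dose difference inside the group that is now pooled.

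The cost is a few contrast statements and some table rows, with no new data or subjects. Each dose-matched interval is about 22% wider than the planned one. The averaged duration contrast is about 13% narrower (0.107/0.124 = 0.87), so precision is not a reason to keep the pooled comparator. More exploratory p-values will be reported; the existing statement in SAP VI.I that such comparisons carry no multiplicity adjustment already covers them.
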